Use of a Red-Rubber Catheter to Facilitate Nasotracheal Intubation in Adult Patients: A Prospective Randomized Controlled Trial

NCT number: NCT03779984

Protocol Date: 02/14/2022

English ICF date: 05/09/2022

**The University of Texas Southwestern Medical Center at Dallas
Institutional Review Board**

Protocol

Use of a Red-Rubber Catheter to Facilitate Nasotracheal Intubation in Adult Patients: A Prospective Randomized Controlled Trial

Institution/Funding Source: Department of Anesthesia and Pain Management – University of Texas Southwestern Medical Center

1. Introduction and Purpose:

Nasotracheal intubation is used to facilitate oropharyngeal surgery in many patients, however, epistaxis is a common complication (1). Several methods to reduce epistaxis during nasotracheal intubation have been studied in adults and children. The use of a red-rubber catheter is effective in guiding nasotracheal intubation in children, however it has not been studied in adults in a prospective, randomized, controlled trial. This study was designed to compare the effectiveness of using a red-rubber catheter versus standard, direct insertion of a thermosoftened, lubricated nasal endotracheal tube into the naris to facilitate nasotracheal intubation in adults undergoing ENT, plastics or OMFS surgery. This study will assess if the red-rubber catheter method leads to lower incidence and severity of epistaxis, and faster time to intubation compared to the current standard of care.

Hypothesis 1 – The red-rubber catheter group will have significantly lower incidence of epistaxis compared to the standard insertion group in patients undergoing nasotracheal intubation.

Primary objective: To compare the incidence of bleeding after nasotracheal intubation.

Hypothesis 2 – The red-rubber catheter group will have significantly lower severity of epistaxis compared to the standard insertion group in patients undergoing nasotracheal intubation.

Secondary objective 1: To compare the severity of epistaxis after nasotracheal intubation.

Hypothesis 3 – The red-rubber catheter group will have significantly fewer airway complications compared to the standard insertion group in patients undergoing nasotracheal intubation.

Secondary objective 2: To compare the rate of complications during nasotracheal intubation.

Hypothesis 4 – The red-rubber catheter group will have significantly lower time to intubation than the standard insertion group.

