The study population for this prospective randomized controlled trial will consist of male and female adult subjects over the age of 18 having surgery requiring NTI. Consent will be obtained by study personnel. Eligible patients will be screened by study personnel up to 1 week prior to scheduled surgery. Informed consent will be obtained in the preoperative holding area. This is a multicenter study. The MD Anderson Center is other site of the study. Each study site will enroll 56 subjects. A total of 112 subjects will be randomized to either the RRC group or control group. Oxymetazoline nasal spray will be administered with 1 spray per nostril preoperatively. Premedication with glycopyrrolate 0.2 mg and benzodiazepine at discretion of provider will be given preoperatively. Subjects will then be brought into the operating room and placed on all standard ASA monitors (BP cuff, EKG, pulse oximetry). One spray of oxymetazoline per nostril will again be administered. Standard preoxygenation will be used with a face mask and 100% O₂. After induction of anesthesia, provider will confirm mask ventilation and 1 more spray of oxymetazoline will be administered per nostril. Intubation will first be attempted via a naris (13). Size 6.5 nasotracheal RAE tubes (Shiley Nasal RAE Tracheal Tube with TaperGuard Cuff, manufactured by Covidien llc, Mansfield, MA 02048) will be used in female patients and size 7.5 in males (16). The tubes will be thermosoftened by allowing them to sit in warm saline prior to use (18). Water-based lubrication will be used for dilation and intubation. Time from insertion of RRC or NETT into nasal passage to first recording of end-tidal CO₂ will be recorded. Direct video laryngoscopy will be used to facilitate placement of the nasotracheal RAE tube. Five minutes after intubation, a non-collaborating anesthesia provider blinded to the method of intubation will grade the severity of bleeding by performing direct video laryngoscopy, inspecting the posterior pharynx and using a scale described originally by Sugiyama et al (19) and again by Earle et. al (20)- no epistaxis (no blood observed on either the surface of the tube or the posterior pharyngeal wall); mild epistaxis (blood apparent on the surface of the tube or posterior pharyngeal wall); moderate epistaxis (pooling of blood on the posterior pharyngeal wall); and severe epistaxis (a large amount of blood in the pharynx impeding nasotracheal intubation—before the epistaxis assessor enters the

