operating room, requiring suction for intubation or necessitating urgent orotracheal intubation.) Degree of nasal pain on the side of intubation will be rated on a numerical rating scale at 30 and 60 minutes in the post-anesthesia care unit (9).

The removal/reinsertion of the laryngoscope and endotracheal tube or switching of the laryngoscopist will be evaluated as a new intubation attempt.

The study duration starts from operating room preoperative holding area admission to discharge from the Post Anesthesia Care Unit (PACU).

RRC group: The funnel end of a RRC (Bard All-Purpose Urethral Catheter, manufactured by C. R. Bard, Inc, Covington, GA 30014 USA) will be securely attached to a room-temperature nasotracheal tube. A 20 Fr RRC will be used with the size 7.5 nasotracheal RAE tube and an 18 Fr RRC will be used with the size 6.5 nasotracheal RAE tube. The tubes will be warmed in saline prior to use (18). Water-based lubrication will be applied to the RRC. The rounded end of the catheter will be introduced into a naris and advanced to the posterior oropharynx and visualized with a laryngoscope. The catheter will then be removed from the end of the nasotracheal tube and withdrawn through the mouth. The nasotracheal tube will then be guided into the trachea past the vocal cords under direct visualization with CMAC video laryngoscope MAC 3 or 4 blade with or without the assistance of Magill forceps as determined by the provider (17).

Control group: The NETT will be warmed in saline prior to use (18). Water-based lubrication will be applied on the nasotracheal RAE tube. The nasotracheal tube will be inserted into the nasal passage and advanced into the oropharynx. The nasotracheal tube will then be guided into the trachea past the vocal cords under direct visualization with CMAC video laryngoscope MAC 3 or 4 blade with or without the assistance of Magill forceps as determined by the provider.

Outcome Measures:

- Incidence of bleeding in posterior oropharynx
- Severity of bleeding in posterior oropharynx
- Need to suction the posterior oropharynx to facilitate intubation
- Time from first insertion of catheter or nasal RAE tube to ETCO₂
- Number of intubation attempts
- Recruitment of the other naris for intubation
- Use of Magill forceps to facilitate intubation
- Use of rescue technique (fiberoptic, oral intubation) to facilitate intubation
- Patient rating of nasal pain on side of intubation
- Anesthesiologist intervention outside of protocol

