- Premature termination of procedure
- Unplanned hospital admission
- Unanticipated complications

4. Study Procedures:

- Identify and screen patients for study eligibility based on inclusion and exclusion criteria.
- Randomize subjects to the RRC or control group in a 1:1 ratio according to a computer-generated block randomization list (multi-center). (Research only)
- Administer premedication in the preoperative area (standard of care)
- Administer 1 spray of oxymetazoline per nostril in preoperative area (standard of care).
- Perform patency test in the preoperative area to determine which nares to use for initial attempt (standard of care).
- All standard monitoring (BP, EKG, and pulse oximeter) will be placed on all patients in the operating room (standard of care).
- Administer 1 spray of oxymetazoline per nostril prior to preoxygenation in the operating room (standard of care).
- Apply standard preoxygenation with full face mask (standard of care).
- Patients will undergo standardized NTI facilitated by RRC or direct insertion based on study group. Both procedures for nasal intubation are considered standard of care.
- Time from insertion of RRC or NETT into nasal passage to first recording of end-tidal CO₂ on monitor will be recorded (standard of care).
- Incidence and severity of epistaxis will be graded by a member of the anesthesia team according to a scale previously described and recorded (19, 20) (Research only).
- Anesthesia providers will record the number of intubation attempts, recruitment of the other naris, premature termination of the procedure, use of Magill forceps and use of rescue techniques to facilitate intubation, and other interventions, complications, or deviations from protocol during intubation in the EMR using a quick note.
- Postoperatively patients will be asked to rate their level of nasal pain on the side (left or right) that NTI was performed using a numerical rating scale at 30 and 60 minutes post emergence from anesthesia. Pain will be evaluated with Numeric Rating Scale (0=no pain and 10- worst pain imaginable). (Research only).

5. Sub-Study Procedures:

- N/A

6. Criteria for Inclusion of Subjects:

- Age > 18, male and female
- Subjects undergoing surgery requiring NTI
- ASA 1-3

7. Criteria for Exclusion of Subjects:

- History of anticoagulant use or coagulopathy
- History of latex allergy
- History of difficult airway
- Anticipated difficult airway requiring awake intubation

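### Does the red-rubber catheter (RRC) arm use an unwarmed tube, and do the differing oxymetazoline lists leave the treatment undefined?

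*Combined protocol and SAP*

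**What the plan says.** **Tube temperature.** Section 3 (Concise Summary of Project) has a sentence that is not tied to an arm: "The tubes will be thermosoftened by allowing them to sit in warm saline prior to use (18". The RRC-group paragraph says the funnel end of the catheter "will be securely attached to a room-temperature nasotracheal tube", then gives the catheter sizes, then continues: "The tubes will be warmed in saline prior to use (18). Water-based lubrication will be applied to the RRC". The control-group paragraph says the tube is warmed and does not mention room temperature. Section 1 describes the comparator as "standard, direct insertion of a thermosoftened, lubricated nasal endotracheal tube into the naris" and does not describe the tube used with the catheter.

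**Lubrication.** The RRC paragraph names the catheter. The control paragraph says "Water-based lubrication will be applied on the nasotracheal RAE tube". The general text of Section 3 says "Water-based lubrication will be used for dilation and intubation".

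**Oxymetazoline.** Section 3 gives one spray per nostril preoperatively, another in the operating room, and after induction "1 more spray of oxymetazoline will be administered per nostril". Section 4 (Study Procedures) has a preoperative item and one before preoxygenation, and no post-induction item.

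**Analysis.** Section 15 (Biostatistics) analyses bleeding by intention to treat. It adds a per-protocol analysis that drops patients with protocol violations, without defining a violation.

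**The concern.** The words room-temperature appear in the procedures of one arm only, and that arm is the experimental one. Reference 18, cited for the warming step, has a title linking thermosoftening to less epistaxis, which is the primary endpoint. The background in Section 2 also describes a paediatric trial that treated room-temperature tubes, warmed tubes and the catheter as separate methods, so the distinction is one the authors know.

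If some operators inserted an unwarmed tube behind the catheter, the trial would compare catheter plus stiff tube with softened tube alone. On that mechanism the bias would run against the catheter, so the risk would be a missed effect rather than a false positive.

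The spray lists raise a different worry. With two sites and with patients of non-investigator anesthesiologists eligible, the written procedure has to carry the standardisation. Where a step appears in two forms, a provider following either could regard it as adherent, and the per-protocol set could become uncertain.

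**Working it through.** **1. The plan's sample size.** Inputs from Section 15: control 50%, RRC 24%, two-sided 5%, 80% power, chi-square test, 5% dropout. The mean rate is (0.50 + 0.24)/2 = 0.37.

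n per arm = [1.960 × √(2 × 0.37 × 0.63) + 0.842 × √(0.50 × 0.50 + 0.24 × 0.76)]² / 0.26²
= [1.960 × 0.6828 + 0.842 × 0.6576]² / 0.0676 = 52.9, so 53.

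Total with dropout = 106/0.95 = 111.6, so 112. Both stated figures are reproduced, and nothing in this point touches them.

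**2. Tube state, sentence by sentence.**

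| Place | State of tube |
|---|---|
| Section 3, general text | softened in warm saline before use, all tubes |
| Section 3, RRC group, on attachment | room temperature |
| Section 3, RRC group, later sentence | warmed before use |
| Section 3, control group | warmed before use |
| Section 1, purpose | softened, said of the comparator only |

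Use of a tracheal tube means its insertion. If the tube is at room temperature when the catheter is fitted and is then warmed, every row is true. If it is at room temperature on insertion, the first and third rows are false. Section 1 contradicts neither reading, because it does not describe the tube in the catheter arm. Only the first reading agrees with the whole text, and it gives a warmed tube in both arms.

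**3. Lubrication.** Each arm paragraph names the device that enters the naris first, and the general sentence covers both stages. Tube lubrication in the RRC arm is not spelled out, but nothing excludes it.

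**4. Oxymetazoline.** Section 3 lists 3 administrations and Section 4 lists 2. Section 4 also leaves out induction, confirmation of mask ventilation, tube size, warming and lubrication, and it never says that two is the full number. It also contains a nostril patency test that Section 3 lacks. Neither list is complete by itself. Both apply to every subject regardless of arm.

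**5. What a misreading would cost.** Let f be the share of RRC tubes inserted unwarmed and d the added bleeding risk in those patients. Both are assumptions; the documents give no value for either. RRC rate = 0.24 + f × d. Exact binomial power of the Pearson chi-square test, 53 per arm, control 50%:

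| f | d | RRC rate | Power |
|---|---|---|---|
| 0 | any | 24% | 81% |
| 10% | 4 points | 24.4% | 80% |
| 25% | 8 points | 26% | 74% |
| 50% | 8 points | 28% | 66% |
| 50% | 12 points | 30% | 57% |

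The text read as a whole puts f at or near 0, the first row.

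**The case for a change.** The strongest reply is that the order of attachment and warming is inferred, not written. A provider who reads only the RRC paragraph meets both descriptions within a few lines. Section 4 is headed as the study procedures, itemises the two earlier sprays separately and does not refer back to Section 3. Neither tube temperature nor the number of sprays is among the items the protocol names for recording, so actual practice might not be recoverable afterwards. Clarifying the wording would cost almost nothing.

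Much of this stands as an editorial remark. The order is indeed unstated, and the two spray lists do differ. It does not show a flaw in the comparison:

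- To insert an unwarmed tube, a provider would have to disregard two explicit warming sentences, one of them in the same paragraph.
- The larger power losses need half of the RRC tubes to be handled that way. They also assume that the planned 24% refers to warmed tubes, for which Section 15 gives no source. Section 2 explains the catheter's benefit as shielding the mucosa from the stiff edge of the tube, so tube stiffness may matter less in this arm.
- A difference in spray practice between providers or sites falls on both randomized arms.
- The per-protocol set is loose because Section 15 never defines a violation. Harmonising these sentences would not cure that, and the primary analysis does not depend on it. Sections 4 and 8 already provide for recording deviations and modifications.

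**Conclusion.** The concern does not call for a change to the plan. Room-temperature is an awkward adjective for the tube at the moment the catheter is fitted; the surrounding text has the tube warmed before insertion in both arms. The lubrication wording is incomplete but not contradictory. The three-versus-two oxymetazoline listings are a real inconsistency between a detailed narrative and a shortened list. They are not specific to an arm and imply no bias in the randomized comparison. Reconciling these passages is a wording matter for the investigators, and this review takes no view on which preparation or number of sprays is right.

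Followed as written, the plan still gives a sound intention-to-treat comparison with its stated 53 per group and 112 in total, and no loss from the planned power. This rests on two assumptions: that operators follow the warming sentences, and that before use means before insertion. Power falls materially only under values of f and d that the documents do not support.

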A designated team of study personnel will be responsible for screening, consenting and enrolling potential subjects. Consenting and enrollment will take place in the preoperative holding area. Information about the study will be given in a pressure-free, confidential private area in a face-to-face meeting and the voluntary nature of the research will be emphasized to the subjects.

The purpose of the study will be explained to the subject. Potential risks and complications will be reviewed. Adequate time will be given for the subject to consider whether to participate in the

study and all questions will be answered by a member of the study team. If the subject agrees to participate, then he or she will sign the consent form and HIPAA Authorization Form prior to any study procedures. In the case of Spanish-only speaking subjects, a live interpreter will be utilized for the above process and the consent and HIPAA Authorization Form will be provided to the subject in Spanish. Subjects will receive a copy of the signed documents.

10. Potential Risks:

This study has minimal risk. The anesthetic management in each group will not differ from the current standard of care.

Risk for RRC: There may be risk for mucosal injury and bleeding with RRC-guided NTI. This risk is not anticipated to be higher than for standard NTI in adults.

Psychological Stress: Some of the questions related to the study may make the subject feel uncomfortable. Subjects may refuse to answer any of the questions, take a break, or stop participation in the study at any time.

Loss of Confidentiality: Any time information is collected; there is a potential risk of loss of confidentiality. Every effort will be made to keep your information confidential.

11. Subject Safety and Data Monitoring:

Investigators will ensure patient safety throughout the procedure. This will include following all standards of care with regard to conducting a safe anesthetic and intubation in the operating room. All standard ASA monitors will be used and proper interventions by the providers will be carried out for complications or difficult intubation. Subjects will recover from the anesthetic in the post-anesthesia care unit. All data will be collected by the anesthesia providers and study personnel.

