Data and Safety monitoring plan includes the formation of a Data and Safety Monitoring Board (DSMB). As independent research expert, Board Certified Anesthesiologists [name] and [name] will review safety and data information. The DSMB will also obtain the results of the interim analysis after 50% enrollment.

12. Procedures to Maintain Confidentiality:

All participants will be given an identification number such that identifiable, personal information will not be used. There will be link to MR number. Subjects will be identified to collect data and verify the data. Every effort will be made to keep all data collection sheets confidential and any electronic data sets will be password protected and secure. Electronic documents will be de-identified according to information security policies. Paper documents will be shredded.

13. Potential Benefits:

There is no benefit to subjects. Use of the RRC may lead to a significant decrease in epistaxis and pain in patients undergoing NTI. Information gained from this study will potentially improve future outcomes in this patient population through reducing complications of nasotracheal intubation.

14. Data Sharing;

MD Anderson site will provide deidentified protocol requiring data via REDCap. UT Southwestern team who have access to MD Anderson Center RedCap will download the de-identified data. REDCap (<https://redcap.mdanderson.org>) is hosted on a secure server by MD Anderson Cancer Center's Department of Oncology Care & Research Information Systems. REDCap has undergone an annual Governance Risk & Compliance Assessment (since May 2014) by MD Anderson's Information Security Office and found to be compliant with HIPAA, Texas Administrative Codes 202-203, University of Texas Policy 165, federal regulations outlined in 21CFR Part 11, and UTMDACC Institutional Policy #ADM0335.

Those having access to the data include the study PI's and research team personnel of both study sites. Users are authenticated against MDACC's Active Directory system. External collaborators are given access to the database once approved by the PI, with their access expiring in 6 months, but renewable in 6 months increments at the request of the PI. The application is accessed through Secure Socket Layer (SSL).

15. Biostatistics: (omit this section for peer-reviewed research such as cooperative group, or NIH- sponsored studies, and for industry-sponsored research which has been submitted to FDA)

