Assuming the incidence of bleeding to be 50% and 24% in the control and RRC group, respectively, a sample size of 53 subjects per group (total n=106) are needed. This study is designed to have 80% power with alpha = 5%, two-sided. Assuming a dropout of 5%, a total of 112 subjects (56 in each arm) are required for this study. The sample size calculation was based on the chisquare tests.

Baseline characteristics (Demographics, Comorbidities) of all randomized patients will be summarized and presented in tables. Categorical variables will be presented as proportions and continuous variables as mean (SD) or median (range) as appropriate. The baseline differences between the two treatment arms will be assessed by Chi square/Fisher exact tests for proportions and Student t-test/Wilcoxon ranksum test for continuous variables as appropriate.

An intention to treat analysis will be conducted to assess the primary endpoint of bleeding. Logistic regression analysis will be conducted to model the primary endpoint between the treatment groups accounting for other confounders. Individual logistic regressions analyses will be conducted to model the secondary outcomes adjusting for treatment groups and other confounders. A univariate and a multivariable linear regression analysis will be conducted for those secondary outcomes, which are measured as continuous variables. A per protocol analysis will also be conducted where

patients with protocol violations will be excluded from the analysis. All analyses will be done using SAS 9.4 and $p < 0.05$ will be considered statistically significant.

15. References:

1. Chauhan, V. and Acharya, G. (2016) Nasal Intubation: A Comprehensive Review. *Indian Journal of Critical Care Medicine*, 20,662-667. doi:10.4103/0972-5229.194013
2. Hall, C.E. and Shutt, L.E. (2003) Nasotracheal Intubation for Head and Neck Surgery. *Anaesthesia*, 58, 249-256. doi:10.1046/j.1365-2044.2003.03034.x
4. Prasanna, D. and Bhat, S. (2014) Nasotracheal intubation: an overview. *Journal of Maxillofacial and Oral Surgery*, 13, 366-372. doi:10.1007/s12663-013-0516-5

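### Section 11 commits to an interim analysis at half enrolment but Section 15 gives no rule for it: two-sided error is about 8.3% if an unadjusted p<0.05 on bleeding could support a claim there, and about 5% if no claim can follow

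*Combined protocol and SAP*

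**What the plan says.** Section 11 sets up a Data and Safety Monitoring Board whose members "will review safety and data information", and adds: "The DSMB will also obtain the results of the interim analysis after 50% enrollment". With 112 subjects planned, that is a look at 56.

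Section 15 is the only statistical section. It assumes bleeding in 50% of controls and 24% of the catheter group, and arrives at 53 per group, raised to 56 for 5% dropout. It says: "This study is designed to have 80% power with alpha = 5%, two-sided" and "The sample size calculation was based on the chisquare tests". For the primary analysis it says: "Logistic regression analysis will be conducted to model the primary endpoint between the treatment groups accounting for other confounders". It closes by setting 0.05 as the significance level for all analyses. It does not mention the interim analysis, and no other section gives the look an endpoint, a purpose, a threshold or a permitted decision.

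Two other places bear on the point. Section 10 (Potential Risks) names bleeding as a risk of the catheter itself: "There may be risk for mucosal injury and bleeding with RRC-guided NTI". Section 3 (Concise Summary of Project) fixes when the outcome is known: "Five minutes after intubation, a non-collaborating anesthesia provider blinded to the method of intubation will grade the severity of bleeding".

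**The concern.** Bleeding is both the primary endpoint and the named risk of the study technique, so a board reviewing safety has good reason to compare it between arms. Because it is graded within minutes of intubation, essentially all subjects enrolled by the look will have a primary outcome, and about half of the final information will be in hand.

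Comparing the arms does not by itself raise the type I error. The gap is that nothing says whether an interim p<0.05 may be used to declare a difference. The plan's only significance level is 0.05. Applied at the look and again at the end, it gives two chances of a false positive at a level meant for one. A rule written after the interim result has been seen could not be shown to be independent of it.

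**Working it through.** **Inputs.** From Section 15: 50% v 24%, two-sided alpha 0.05, power 80%, chi-square test, 53 per group, 5% dropout, 112 in total. From Section 11: one look at 50% enrolment. From Section 4 (Study Procedures): 1:1 block randomization, so I take equal arms at the look, 28 then 56 per arm.

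**1. The plan's own sample size.** With pooled variance under the null and no continuity correction,

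n = [1.960·√(2·0.37·0.63) + 0.842·√(0.50·0.50 + 0.24·0.76)]² / 0.26²
= (1.960·0.6828 + 0.842·0.6576)² / 0.0676 ≈ 52.9, so 53 per arm.

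106 / 0.95 = 111.6, so 112. The stated figures reproduce as a fixed design with one test. There is no allowance for a look.

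**2. Two unadjusted tests, normal theory.** At half the information the two test statistics have correlation √0.5. The overall error is 1 − P(|Z₁|<c₁, |Z₂|<c₂).

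| Rule (interim, final) | c₁, c₂ | Overall two-sided error |
|---|---|---|
| 0.05, 0.05 | 1.960, 1.960 | 8.31% |
| Haybittle-Peto: 0.001, 0.05 | 3.291, 1.960 | 5.02% |
| O'Brien-Fleming: 0.0052, 0.0480 | 2.797, 1.977 | 5.00% |

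The first row moves little with timing: 8.5% at 45% information and 8.1% at 55%.

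**3. Exact check.** Binomial enumeration over common bleeding rates of 24% to 50% in 1-point steps. The second column assumes 5% dropout, with 26 or 27 per arm at the look. The third uses a treatment-only logistic Wald test as a stand-in for the planned model, whose confounders are not named.

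| Rule | Chi-square, 28 then 56 | Chi-square, 26 or 27 then 53 | Logistic Wald, 28 then 56 |
|---|---|---|---|
| Final test only | 4.6% to 5.2% | 4.4% to 5.3% | 4.5% to 4.8% |
| 0.05 twice | 7.7% to 8.6% | 7.1% to 9.0% | 7.1% to 7.8% |
| Haybittle-Peto | 4.7% to 5.2% | 4.4% to 5.4% | 4.5% to 4.8% |
| O'Brien-Fleming | 4.7% to 5.1% | 4.4% to 5.3% | 4.5% to 4.9% |

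**4. Under the planned 50% v 24%.**

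| Rule | Interim crossing, chi-square, 28 per arm | Power, chi-square, 56 per arm | Power, chi-square, 53 per arm |
|---|---|---|---|
| Final test only | none | 82.4% | 81.1% |
| 0.05 at the look | 53% | not a proposed rule | not a proposed rule |
| Haybittle-Peto | 9% | 82.4% | 81.1% |
| O'Brien-Fleming | 20% | 81.7% | 80.6% |

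With the Wald stand-in at 28 per arm, the crossing chances are about 50.5%, 6% and 18%. At 53 evaluable per arm, Wald power is 80.5% with one test and 79.8% with O'Brien-Fleming.

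**The case against.** The 8.3% depends on steps that the protocol does not state: that the look tests bleeding between arms, that it does so at an unadjusted 0.05, that a claim could follow, and that a second test at 0.05 comes later. The sentence sits in the safety section, and early stopping or an early efficacy report is mentioned nowhere. The 0.05 level closes a list of analyses that does not include the interim, so applying it there is an inference. On the plainest reading, one test is made at the end and the error is about 5%.

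This is a fair reading and it limits the finding: the inflation is conditional, not demonstrated. It does not close the gap, because the text neither states the safety-only reading nor excludes the other one.

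Three smaller points also stand:
- The 53% assumes the full planned effect and a chi-square test with 28 per arm. With 26 or 27 per arm it is 51% to 52%, and with the Wald stand-in it is 48% to 51%. It remains about an even chance.
- O'Brien-Fleming with the Wald stand-in at 53 per arm falls just under the 80% target.
- If the look is meant for safety, the no-claim wording suits the protocol better than a boundary.

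**Conclusion.** The concern holds as a conditional one. The omission is certain: the protocol commits to an interim analysis and gives no rule for it. Its size depends on what the look may be used for. If an unadjusted p<0.05 could support a claim, the overall two-sided error is 8.3% (7.7% to 8.6% exact), about 3 points above the stated 5%. If no claim can follow, it is about 5%.

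These figures assume one look at about half the information, equal arms, and the same two-sided test at both times. The planned logistic model cannot be reproduced exactly because its covariates are not named. The treatment-only stand-in gives 7.1% to 7.8% and leads to the same conclusion. The point should be settled before any interim comparison is seen.

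**What to change.** Name the interim analysis in Section 15 and adopt one of two statements.

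- **If an early claim is intended:** efficacy on bleeding may be claimed at 56 subjects only if two-sided p<0.001 (Haybittle-Peto), with the final test at 0.05. O'Brien-Fleming levels of 0.0052 and 0.0480 are an acceptable alternative.
- **If no early claim is intended:** *No efficacy claim will be made at the interim analysis. The DSMB may compare bleeding between arms for safety, any futility guidance is non-binding, and the final test stays at two-sided 0.05.*

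Either is a change of wording and needs no extra subjects. The cost of a boundary is a stricter interim threshold: under 50% v 24% the chance of an early claim (chi-square) falls from about 53% to about 9% with Haybittle-Peto or 20% with O'Brien-Fleming. Power is essentially unchanged with Haybittle-Peto and less than 1 point lower with O'Brien-Fleming. The no-claim option gives up any early claim and leaves the final test and its power as planned.
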